5.1.1.6 Phase II treatment schedule for patients NOT participating in the surgical substudy

Temsirolimus: The starting dose for temsirolimus will be determined from the phase I component. There is no intra-patient dose escalation.

Perifosine: The starting dose (load and maintenance) for perifosine will be determined from the phase I component. The loading dose is only administered during cycle 1 unless treatment is interrupted for >7 days for which patients will receive a repeat loading dose upon restarting perifosine ([table](#)). There is no intra-patient dose escalation.

Treatment with both agents will occur simultaneously in the following manner: after anti-emetic prophylaxis, patients will receive the first divided dose of the perifosine loading dose. Patients will be observed for 30 minutes to ensure there has been adequate anti-emetic prophylaxis, and then patients will receive temsirolimus administered over 30 minutes IV. The remaining divided doses of the perifosine loading dose will then be administered. Patients will then return weekly for infusion of temsirolimus over 30 minutes IV. Dosing will

Memorial Sloan Kettering Cancer Center
IRB Protocol

IRB#: 09-058 A(14)

be continuous although for the purposes of evaluation, a cycle will be defined as 4 weeks (28 days). It is expected that temsirolimus administration will occur on the same day of the week throughout the treatment period. However, it may be given up to 3 days early or late due to holiday or other scheduling reasons.

Prior to beginning cycle 3, patients undergo clinical and radiographic tumor restaging. As long as the tumor is stable or smaller in size and the patient is clinically stable or improved, they will go on 2 more 4 week cycles of therapy with temsirolimus and perifosine. Treatment will continue indefinitely as long as there are no unacceptable toxicities (DLTs) and no clinical or radiographic progression.

5.1.1.7 Phase II treatment schedule for patients who **ARE** participating in the surgical substudy

Patients who choose to participate in this component of the study must have a contrast enhanced brain MRI performed within 14 days of taking pre-operative temsirolimus and perifosine. Patients unable to undergo MRI will have CT scans. A brain PET scan must also be performed within the 14 days before taking pre-operative temsirolimus and perifosine, and again (research PET) after completing the full loading dose of perifosine and 1 dose of temsirolimus but before surgery to correlate metabolic effects with tissue analysis. A repeat PET is again requested but is not mandatory for patients with residual measurable disease post-operatively before restarting study drugs (research PET).

Before surgery

The loading dose of perifosine and the dose of temsirolimus will be administered on the same day. This may be up to 1-4 days pre-operatively

Temsirolimus: Patients will receive one treatment of temsirolimus intravenously prior to surgery analogous to phase II patients NOT on the surgical substudy ([section 5.1.1.6](#)). The dose will be determined by the phase I component of the study. This dose of temsirolimus may be administered up to the 4th pre-operative day. This dosing allows for some flexibility in scheduling surgery.

Perifosine: Patients will receive a loading dose of perifosine prior to surgery analogous to phase II patients NOT on the surgical substudy ([section 5.1.1.6](#)). Patients will receive a loading dose of perifosine the same day they receive pre-operative temsirolimus. They will receive a maintenance dose nightly starting the next day until the night before surgery. If the loading dose is administered on the pre-operative day, then they will not receive a maintenance dose pre-operatively. The dose will be determined by the phase I component of the study.

Both agents should be administered as in [section 5.1.1.6](#). **Both agents should be started up to 4 days before surgery. If clinical or other scheduling reasons alter the plan or timing for surgery, the PI must be notified and best physician practice applied to care for the patient.**

Day of surgery

Tissue freezer vials should be labeled with the patient's protocol study Identifier number(s). Additionally, a thermos with liquid nitrogen (preferably), or if not possible, an ice bucket with dry ice should be prepared. All attempts will be made to obtain specimens immediately adjacent to the areas of resection taken for "permanent sections" in order to optimize the likelihood that the tumor seen on permanent sections is representative of that taken for analysis. Once the pathologist has made a diagnosis of "tumor" on frozen section at the time of surgical resection, the tumor tissue should be divided into 50 – 100mg pieces.

At the time of surgical resection, the following specimens will be obtained:

- Fresh tumor tissue frozen in liquid nitrogen for evaluation of activation status of PI3K/AKT/mTOR/S6K, RAS/MEK/ERK, proliferation, and gene profiling.

Amended:

Reviewed by OCR, JR 3/24/14

Memorial Sloan Kettering Cancer Center
IRB Protocol

IRB#: 09-058 A(14)

- Paraffin block or slides for evaluation of activation status of PI3K/AKT/mTOR/S6K, RAS/MEK/ERK, proliferation, apoptosis, and gene profiling.

It is important that the exact times of collection of these specimens be recorded.

Pre and post-operative evaluations will consist of standard clinical practice. Patients should have weekly CBC and differential in the postoperative period. Once patients have recovered from the effects of surgery, they will start the phase II component of the study. Patients are not required to have residual disease to continue onto the phase II component.

Following surgery

A post-operative MRI/CT scan should be done no later than 96 hours from surgery on a steroid dose that is stable or decreasing. Treatment with temsirolimus and perifosine post-operatively should start no later than 14 days after the scan. If the 96-hour scan is more than 14 days before treatment is initiated, the scan needs to be repeated on a stable or decreasing steroid dose. The post-operative scan should be assessed for the presence of residual measurable disease. A repeat PET is again requested but is not mandatory for patients with residual measurable disease post-operatively before restarting study drugs.

Treatment may be instituted starting 7 days postoperatively if patients have recovered from effects of surgery and demonstrated wound healing. Treatment with temsirolimus and perifosine post-operatively should start no later than 56 days after surgery.

Day 1 of treatment following surgery will represent the first day of treatment for determination of the primary endpoint of 6 month progression free survival. The dose of temsirolimus and perifosine will be determined by the phase I component of the study. Patients will undergo a loading dose of perifosine when re-initiating treatment post-operatively. Patients will receive treatment in 4 week cycles in the same manner as patients not on the surgical substudy. Drug treatment will be started analogously to patients in the phase II component NOT on the surgical substudy.

In the unlikely event that the analysis of the tissue specimen demonstrates necrosis or lack of active disease, the PI should be notified and the patient disenrolled from the trial as they are not eligible without recurrent/progressive disease. Such patients may be replaced.

5.1.2 Other Agents: N/A

5.1.3 Other Procedures

5.1.3.1 Pre-treatment evaluations

A complete history, physical, and neurological examination (to include documentation of the patients Karnofsky Performance Status per [Appendix A](#), as well as neuro-imaging confirming tumor progression shall be performed on all patients. The baseline scan should be performed within 14 days of treatment initiation. Brain PET (to evaluate tumor metabolism) should be performed as well for patients on phase II.

Prestudy laboratory tests shall include CBC, differential, platelets, PT, PTT, INR, carbon dioxide, BUN, creatinine, glucose, potassium, sodium, calcium, phosphorus, chloride, total protein, albumin, alkaline phosphatase, total bilirubin, SGOT (AST), SGPT (ALT), uric acid, cholesterol, triglycerides. Antiepileptic drug levels may be drawn if they are used clinically to monitor patient's AED dose. These pr-study laboratory tests must be obtained within 14 days of treatment initiation. Women of childbearing potential must obtain a serum pregnancy test within 7 days prior to registration.

Unstained paraffin tissue from surgical samples: Every reasonable effort will be made to obtain a

Amended:

Reviewed by OCR, JR 3/24/14

Memorial Sloan Kettering Cancer Center
IRB Protocol

IRB#: 09-058 A(14)

representative paraffin tissue block (at least 5 mm x 5 mm) or at least 15 unstained paraffin slides (preferably 30) in all patients from original surgery and/or definitive surgery and/or the surgery closest to initiation of this clinical trial in patients on phase I. Prior tissue is mandatory for patients on phase II. Paraffin slides will be used for DNA isolation and immunohistochemistry to evaluate molecular pathways described in [section 2.5](#) and [section 9](#). Array comparative genomic hybridization (array CGH) will also be performed on these specimens. We will attempt to correlate tumor genotype with response to treatment.

5.1.3.2 Evaluation during study: Phase I requirements

Following the 1st treatment, CBC, differential, and platelets, and serum chemistries (BUN, creatinine, glucose, calcium, alkaline phosphatase, phosphorus, total bilirubin, SGOT (AST), SGPT (ALT), fasting cholesterol and triglycerides will be performed every week for the first 4 weeks and then every 2 weeks thereafter. All labs are permitted to be obtained up to 3 days prior to the weekly Temsirolimus IV infusion. AED levels (if clinically appropriate) will be measured every 2 weeks for the first 4 weeks and then every 4 weeks. β -HCG will be measured prior to each 4-week cycle. For patients on warfarin, a PT/INR will be checked every 1-2 weeks, or sooner if clinically indicated. Uric acid will be re-checked as clinically indicated.

A head CT (without contrast) or MRI with gradient echo must also be performed during week 2 of treatment to evaluate for subclinical hemorrhage observed in mice treated with the combination of temsirolimus and perifosine.

A brain MRI/CT will be done prior to every other cycle (up to 2 weeks prior). An MRI/CT scan done at 6 months from initiation of therapy will be performed while the patient is still in the study to ensure assessment of the primary endpoint.

A complete physical and neurologic exam (to include documentation of the patients Karnofsky Performance Status) will be performed up to 3 days prior to every cycle.

Phase I patients will be evaluated for adverse events at least weekly during their first cycle of therapy. These adverse events will be reported to the PI.

Adverse events for subsequent cycles will be reported prior to the beginning of each cycle. In addition all serious adverse events will be reported to the NCI and the PI.

All relevant information regarding drug doses, concomitant medications, and doses, measurable lesions with measurements, tumor response, laboratory examinations, and treatment-related toxicities shall be documented in the patient's medical record and flow sheets.

All patients will be followed for overall survival, when possible.

- Patients who discontinue treatment due to progression will be followed for survival every 3 months.
- Patients who come off therapy for reasons other than progression should be followed until progression or institution of new anti-tumor therapy. They should then be followed for survival.

5.1.3.3 Evaluation during study: Phase II requirements

Following the 1st treatment, CBC, differential, and platelets, and serum chemistries (BUN, creatinine, glucose, calcium, alkaline phosphatase, phosphorus, total bilirubin, SGOT (AST), SGPT (ALT), fasting cholesterol and triglycerides will be performed every week for the first 4 weeks and then every

Amended:

Reviewed by OCR, JR 3/24/14

Memorial Sloan Kettering Cancer Center
IRB Protocol

IRB#: 09-058 A(14)

2 weeks thereafter. All labs are permitted to be obtained up to 3 days prior to the weekly Temsirolimus IV infusion. Patients with normal bloodwork may have these laboratory tests performed every 4 weeks after the first 16 weeks. AED levels (if clinically appropriate) will be measured every 2 weeks for the first 4 weeks and then every 4 weeks. β -HCG will be measured prior to each 4-week cycle. For patients on warfarin, a PT/INR will be checked every 1-2 weeks, or sooner if clinically indicated. Uric acid will be re-checked as clinically indicated.

A head CT (without contrast) or MRI with gradient echo must also be performed during week 2 of treatment to evaluate for subclinical hemorrhage observed in mice treated with the combination of temsirolimus and perifosine. Note that the CT of the head performed with the PET scan (i.e., in patients undergoing a PET/CT) is NOT sufficient.

A brain MRI/CT will be done prior to every other cycle (up to 2 weeks prior). A brain MRI/CT done at 6 months from initiation of therapy will be performed while the patient is still in the study to ensure assessment of the primary endpoint.

A brain PET scan for research purposes will be performed after 1-2 weeks of treatment. A follow up PET will then be performed after every 4th cycle (approximately 16 weeks). The PET scans must be performed at MSKCC in order to allow easier comparison and interpretation.

A complete neurologic exam (to include documentation of the patients Karnofsky Performance Status) will be performed up to 3 days prior to every other cycle.

Phase II patients will be evaluated for adverse events at the end of each cycle. In addition all serious adverse events will be reported to the NCI and the PI.

All relevant information regarding drug doses, concomitant medications, and doses, measurable lesions with measurements, tumor response, laboratory examinations, and treatment-related toxicities shall be documented in the patient's medical record and flow sheets.

All patients will be followed for overall survival, when possible.

- Patients who discontinue treatment due to progression will be followed for survival every 3 months.
- Patients who come off therapy for reasons other than progression should be followed until progression or institution of new anti-tumor therapy. They should then be followed for survival.

Patients enrolled in surgical substudy must have a brain MRI/CT scan obtained within 96 hours post-operatively. Treatment with temsirolimus and perifosine post-operatively should start no less than 7 days and no later than 56 days after surgery. If post-operative scan (performed within 96-hour after surgery) is more than 14 days old when treatment is re-initiated post-operatively, the scan needs to be repeated.

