3 PATIENT SELECTION

3.1 General Eligibility Criteria

- 3.1.1 Patients must have unstained slides or tissue blocks available from at least one prior surgery. Frozen tissue is also requested if available.
- 3.1.2 Patients must have received prior radiotherapy and temozolomide. There is otherwise no limit on the number of prior recurrences/therapies.
- 3.1.3 At least 6 weeks (42 days) must have elapsed since completion of radiation therapy to initiation of study treatment.
- 3.1.4 At least 4 weeks (28 days) must have elapsed since most recent temozolomide and initiation of study treatment.
- 3.1.5 Patients must have recovered from the toxic effects of other prior direct inhibitors of VEGF/VEGFR: 4 weeks from prior therapy with agents such as bevacizumab (Avastin), afibbercept (VEGF-Trap), cediranib (AZD2171), or XL-184 (BMS 907351); any questions regarding the definition of a direct anti-VEGF/VEGFR therapy must be discussed with the PI or co-PI. Patients must have recovered from the toxic effects of other prior therapy including: 4 weeks (28 days) from any investigational agent, two weeks (14 days) from vincristine, 6 weeks (42 days) from nitrosoureas, 3 weeks (21 days) from procarbazine administration, and 1 week (7 days) for non-cytotoxic agents, e.g., interferon, tamoxifen, thalidomide, cis-retinoic acid, etc. (radiosensitizer does not count), and 4 weeks (28 days) from any other prior cytotoxic therapy. Any questions related to the definition of non-cytotoxic agents should be directed to the co-PI.
- 3.1.6 Patients must have shown unequivocal evidence for tumor progression by MRI/CT on the baseline MRI/CT in comparison to a prior scan OR have recently undergone resection for recurrent/progressive disease per 3.1.17. The baseline brain MRI/CT must be performed 14 days or fewer prior to treatment. The same type of scan, i.e., MRI (or CT for patients who cannot undergo MRI) must be used throughout the period of protocol treatment for tumor measurement. Criteria in [section 11](#) for progression on this study are not mandatory if the disease progression is obvious in the opinion of the investigator. Any questions should be addressed to the PI.

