6.1.3 Non-hematologic toxicity

Dose Modifications Based on perifosine and temsirolimus-related Non-Hematologic Toxicities and dose adjustments for each drug shown in [tables 4, 5, and 6](#):

NCI Grade	% of Planned perifosine and temsirolimus dose
0-2+	100%+
3*	hold**
4	hold***

- + For symptomatic Grade 2 toxicity, the dose may be held until recovery to CTC Grade 0-1, then continue at the same dose or reduce by one level of temsirolimus and/or perifosine at the investigator's discretion. Grade 2 diarrhea does not require temporary discontinuation of treatment as this toxicity may improve despite continued treatment. For grade 2 diarrhea that is unacceptable to the patient for symptomatic reasons, hold perifosine temporarily held until resolution \leq grade 1 and subsequently re-started at the same dose. If symptomatic grade 2 diarrhea recurs after re-instituting treatment at the same daily dose and require temporary discontinuation, treatment of both agents should be held until resolution to \leq grade 1 and re-instituted at a reduced doses of both agents (see [Table 4, 5, and 6](#)).
- + In addition, areas of intratumoral micro-hemorrhage were noted on necropsy of mice harboring modeled GBMs following combined treatment of perifosine and temsirolimus. Significance of this in humans is unclear, and it may represent an early response to therapy. However, for patient safety, a non-contrast head CT or MRI with gradient echo imaging is required during the 2nd week of therapy to evaluate for such microbleeds. CTCAE grade 1 (asymptomatic, radiographic findings only) do not require treatment modification. CTCAE grade 2 (medical intervention indicated) may require corticosteroids as treatment for associated edema or other intervention at the discretion of the investigator, but treatment can continue at the discretion of the investigator.

Memorial Sloan Kettering Cancer Center
IRB Protocol

IRB#: 09-058 A(14)

- * Except nausea/vomiting (unless patients are on maximal antiemetic therapy) or hypercholesterolemia and hypertriglyceridemia and other Metabolism and Nutrition Disorders (such as hypophosphatemia and hypocalcemia) unless remaining grade 3 or unacceptable grade 2, despite maximal medical therapy.

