
a: Temsirolimus administered weekly, Perifosine administered daily.
 
b: Following the 1st treatment: Weekly for first 4 weeks and then every 2 weeks. Phase II patients with stable bloodwork after 16 weeks can have these laboratory tests monthly.
 
c: Following the 1st treatment: For patients on warfarin, every 1-2 weeks, or sooner, if clinically indicated; otherwise, at the discretion of the treating physician.
 
d: Following the 1st treatment: Alkaline phosphatase, total bilirubin, carbon dioxide, BUN, calcium, chloride, creatinine, glucose, phosphorus, sodium, potassium, total protein, SGOT[AST], SGPT[ALT] weekly for 4 weeks then every 2 weeks. Phase II patients with stable bloodwork after 16 weeks can have these laboratory tests monthly. Uric acid should be checked at baseline and then during treatment as clinically indicated.
 
e: Patients with diarrhea should have more frequent monitoring of electrolytes at the discretion of the investigator.
 
f: Following the 1st treatment: Fasting triglycerides and cholesterol weekly for first 4 weeks then every 2 weeks. Phase II patients with stable bloodwork after 16 weeks can have these laboratory tests monthly.
 
g: MRI or CT at baseline and every 8 weeks (may be performed up to 2 weeks early). An FDG-PET scan should be performed after 1-2 weeks of therapy and every 4th cycle (16 weeks). A NON-CONTRAST HEAD CT OR AN MRI WITH GRADIENT ECHO SEQUENCE MUST ALSO BE PERFORMED DURING WEEK 2 TO EVALUATE FOR HEMORRHAGE (see 5.1.3).
 
h: Serum pregnancy test (women of childbearing potential).
 
i: Note: all tests and evaluations performed for baseline can also serve as those required for week 1, as long as they are within the starting timeframes of treatment initiation.
												

NOTE: All laboratory tests, assessments, and treatments are permitted a window of +/- 3 days to accommodate patient scheduling, weekends, and/or holidays
												

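### The week 2 hemorrhage scan has no required blood-sensitive baseline, so blood already present cannot be reliably separated from treatment-emergent bleeding

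*Combined protocol and SAP*

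**What the plan says.** **Week 2.** Sections 5.1.3.2 (phase I) and 5.1.3.3 (phase II) carry the same requirement: "A head CT (without contrast) or MRI with gradient echo must also be performed during week 2 of treatment to evaluate for subclinical hemorrhage". The stated reason is hemorrhage seen in mice given the combination. Section 6.1.3 repeats it: "a non-contrast head CT or MRI with gradient echo imaging is required during the 2nd week of therapy to evaluate for such microbleeds". Calendar note g in Section 10 does too: "A NON-CONTRAST HEAD CT OR AN MRI WITH GRADIENT ECHO SEQUENCE MUST ALSO BE PERFORMED DURING WEEK 2 TO EVALUATE FOR HEMORRHAGE". Section 5.1.3.3 adds that the head CT acquired with a PET/CT does not count for this check.

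**Baseline.** Section 3.1.6 says "The baseline brain MRI/CT must be performed 14 days or fewer prior to treatment". Section 5.1.3.1 says "The baseline scan should be performed within 14 days of treatment initiation" and gives the purpose as confirming progression. Calendar note g says "MRI or CT at baseline and every 8 weeks (may be performed up to 2 weeks early". None of these names gradient echo or a non-contrast series.

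**Surgical substudy.** Section 5.1.1.7 says patients "must have a contrast enhanced brain MRI performed within 14 days of taking pre-operative temsirolimus and perifosine", with CT for those who cannot have MRI. After surgery a scan is due within 96 hours and is repeated if it is more than 14 days old at restart. Its stated use is to look for residual measurable disease.

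**Consequences.** Under Section 6.1.3 an asymptomatic, purely radiographic hemorrhage is grade 1 and needs no treatment change.

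**The concern.** A week 2 scan on its own shows whether blood is present, not when it appeared. Pre-existing blood is plausible in this population. Every patient must have tissue from at least one prior surgery and must have had radiotherapy (3.1.1, 3.1.2). Recently resected patients are eligible (3.1.17). Substudy patients may restart from 7 days after surgery (5.1.1.7).

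Characterizing the safety of the combination is a stated objective (1.2.1), and the week 2 scan is the only dedicated imaging check for the bleeding seen in the mouse model. Without a comparator, old blood may be recorded as drug-related, or new blood set aside as old. Section 2.1 already reports CNS bleeding on temsirolimus, mainly in patients with CNS tumors, with causality left unclear because several were taking anticoagulants. An uncompared scan would leave the same kind of ambiguity.

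**Working it through.** The plan states no hemorrhage rate or threshold, so there is no figure to reproduce. The check is a comparison of requirements, followed by an illustration.

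**Step 1. Requirements side by side.**

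| Time | Section | Imaging required | Blood-sensitive technique required? |
|---|---|---|---|
| Baseline, all patients | 3.1.6, 5.1.3.1, 10 note g | MRI or CT within 14 days | No |
| Baseline, substudy, pre-operative | 5.1.1.7 | Contrast-enhanced MRI (CT if MRI is not possible) | No |
| Substudy, before restart | 3.1.20, 3.1.21, 5.1.1.7, 5.1.3.3 | MRI or CT, type unspecified | No |
| Week 2, both phases | 5.1.3.2, 5.1.3.3, 6.1.3, 10 note g | Non-contrast CT or gradient-echo MRI | Yes |

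**Step 2. Do the same-technique rules close the gap?** Section 3.1.6 says the same type of scan "must be used throughout the period of protocol treatment for tumor measurement", so it is limited to tumor measurement. Section 11.1 asks for consistency between CT and MRI within a patient, and 11.3 asks for a consistent method for each reported lesion. Both stand in the efficacy section and neither names a sequence. A patient may therefore have a contrast MRI at baseline and a non-contrast CT at week 2. No text says how to handle blood already present.

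**Step 3. Timing in the substudy.** Section 11.2 counts treatment from the first post-operative dose. With a restart on post-operative day 7, treatment days 8 to 14 are post-operative days 14 (7 + 7) to 20 (7 + 13). The week 2 scan can thus fall within three weeks of a craniotomy. Up to 10 patients may enter this substudy.

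**Step 4. What depends on the distinction.**
- Grade 1: no treatment change (6.1.3), no DLT criterion met (5.2.1), and no expedited report in either phase (reporting tables in Section 7).
- Grade 2: intracranial hemorrhage is listed for both agents only among events of undetermined relationship (7.1.1, 7.1.2), not among the reporting exceptions. An unexpected grade 2 event judged at least possibly related needs a 10-day report; one judged unlikely or unrelated does not.
- DLT status also requires attribution (5.2.1).

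The distinction therefore affects counting and attribution. An asymptomatic finding is grade 1 whether the blood is old or new.

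**Step 5. Illustration with assumed inputs.** Let q be the share of patients with pre-existing blood visible at week 2, and t the probability of a new bleed by then. The documents give neither. Assume that they are independent, that all blood present is seen, and that the same q applies to both techniques.

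- P(week 2 positive) = 1 − (1 − q)(1 − t)
- Share of positives with no new bleed = q(1 − t) / [1 − (1 − q)(1 − t)]

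The planned 42 phase II patients (20 + 22) give:

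| q | t | Positive | Of 42 | With no new bleed | Share of positives |
|---|---|---|---|---|---|
| 5% | 10% | 14.5% | 6.1 | 1.9 | 31% |
| 20% | 10% | 28% | 11.8 | 7.6 | 64% |
| 50% | 10% | 55% | 23.1 | 18.9 | 82% |
| 20% | 0% | 20% | 8.4 | 8.4 | 100% |

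With t = 10%, about 4.2 patients (42 × 0.10) have a new bleed in each of the first three rows. Without a comparator they are not distinguishable by design from the other positives.

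**The case against.** The strongest reply is that the week 2 scan is a safety screen for bleeding that matters at the time, not an incidence endpoint. Section 13 sets no hemorrhage rate, threshold or stopping rule, and safety data are summarized descriptively. A screen can do that job without a matched baseline. This stands, and it limits the weight of the point. It does not answer how a positive scan is to be counted or attributed.

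A reader might also infer more than the documents support:

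- *That there is no baseline, or that old and new blood can never be told apart.* A baseline MRI or CT is mandatory, and substudy patients have a post-operative scan. A site may include gradient echo by habit, and a radiologist may be able to date some blood. What is missing is a requirement.
- *That CTCAE grades would be wrong.* Section 6.1.3 grades by symptoms and need for intervention, so the age of the blood does not change the grade of an asymptomatic finding.
- *That week 2 is the only human evidence on bleeding.* Brain imaging is repeated before every other cycle. Adverse events are assessed weekly in phase I cycle 1 and at the end of each cycle in phase II.
- *That the week 2 technique must match baseline.* Most patients will have a baseline MRI, since 3.1.6 reserves CT for those who cannot have one. Mandatory matching would remove their CT option at week 2 or call for an additional baseline CT, which is not a small cost.

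**Conclusion.** The omission is confirmed in both phases: the protocol requires a blood-sensitive technique at week 2 and none before treatment or before the substudy restart. Hemorrhage findings at week 2 therefore cannot be reliably classed as treatment-emergent.

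The effect is confined to counting and attribution of hemorrhage as an adverse event. The primary endpoint, the sample size and the two-stage rule are untouched, and asymptomatic findings trigger no treatment change. The 31% to 82% range rests entirely on assumed values of q and t, on independence and on complete detection; it shows how the ambiguity scales and is not an estimate for this trial. The point merits a change because the remedy is small and a pre-treatment scan cannot be obtained once dosing has begun.

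**What to change.** - **Section 5.1.3.1 and calendar note g:** state that the baseline MRI already required within 14 days includes a gradient-echo sequence, or that a non-contrast pass is acquired where CT is the baseline modality. Section 5.1.3.1 applies to both phases.
- **Section 5.1.1.7, with 3.1.20, 3.1.21 and 5.1.3.3 to agree:** add the same to the substudy's post-operative scan that serves as the baseline before restart. That scan separates surgical blood from bleeding after restart. It cannot separate surgery from the pre-operative dose, for which the pre-operative scan is the only drug-free reference.
- **Sections 5.1.3.2 and 5.1.3.3:** report week 2 hemorrhage as new or increased relative to that baseline, and record the technique used at each time. Matching the week 2 technique to baseline is preferred where feasible but should not be mandatory, so that no additional scan is forced.

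The cost is a few minutes on a scan already scheduled and short edits to these sections. No visit is added, and no dosing or stopping rule changes.
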